5.8 Treatment of Study Drug Overdose

There are no known antidotes for overdoses of rociletinib or MPDL3280A. In the event of an overdose of MPDL3280A, discontinuation of MPDL3280A may not have immediate therapeutic effect. In the event of a known or suspected overdose, the patient should be monitored with appropriate hematology and clinical chemistry and should receive supportive therapy, as necessary. Please also refer to Section 6 for guidelines on the management of potential study drug-related toxicities.

Decisions regarding dose interruptions or modifications for rociletinib and/or MPDL3280A dosing in the case of a suspected overdose will be made by the Investigator in consultation with the Medical Monitor based on the clinical evaluation of the patient.

A plasma sample for PK analysis may be requested by the Medical Monitor on a case-by-case basis. This plasma sample should be collected as soon as possible, but within 10 days from the date of the last dose of on-study dosing.

Information regarding the quantity of the excess dose as well as the duration of the overdosing should be documented in the appropriate eCRF.

6 MONITORING AND MANAGEMENT OF EXPECTED OR POTENTIAL TREATMENT-RELATED TOXICITY

In general, toxicities should be managed with supportive care and with dose modifications for each of the study drugs (Section 5.7) according to attribution of the toxicity. Certain toxicities may be more likely to occur with rociletinib or MPDL3280A, and some toxicities may be overlapping. This section provides guidance on the monitoring and management of expected or potential toxicities associated with rociletinib or MPDL3280A or both rociletinib and MPDL3280A.

6.1 Rociletinib Expected or Potential Toxicities

6.1.1 Management of Prolonged QTc

Electrocardiograms will be performed throughout the study as described (see Table 1 and Section 8.4.2.4). Readings for QTc prolongation will be based on the average for the triplicate ECGs for each time point. Patients are required to have within-normal-range potassium and magnesium at enrollment, and these electrolytes should be maintained within range during rociletinib treatment, using supplementation if necessary.

Guidelines for dose modification and stopping criteria due to QTc prolongation are provided in Table 9.

QTc-Prolongation ^a	Action and Dose Modification
$QTcF \ge 501$ msec on at least two	• Interrupt study treatment until QTcF prolongation resolves to Grade 1 (QTcF > 450-480 msec) or baseline;
separate ECGs ^a (Grade 3)	• Test serum potassium, calcium, phosphorus and magnesium. If abnormal, correct per routine clinical practice to within normal limits;
	• Review concomitant medication usage for a prolonged QTc;
	• Restart at a reduced dose level ^b ;
	• If Grade 3 QTc prolongation recurs after 2 dose reductions, permanently discontinue study treatment ^b ;
	 If Grade 4 QTc prolongation (QTcF ≥ 501 or 60 msec increase from baseline and polymorphic ventricular tachycardia or serious arrythmia) occurs, permanently discontinue study treatment^b

 Table 9:
 Withholding and Stopping Criteria for QTc-Prolongation

msec, milliseconds; QTcF, QT interval on electrocardiogram corrected using Fridericia's formula (see Appendix D) ^a Based on average QTc value of triplicate ECGs.

^b If the QTc prolongation resolves to Grade 1 or baseline, the patient may resume study treatment if the Investigator and Medical Monitor agree that the patient will benefit from further treatment.

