namics	A mandatory fresh tumor tissue biopsy specimen will be collected within 60 days prior to the first day of study treatment for all patients. In addition, an optional fresh tumor biopsy may be collected at time of permanent treatment discontinuation due to disease progression (at the time the Investigator believes the patient is no longer deriving clinical benefit from study treatment, if treatment beyond radiographic disease progression is approved). The baseline tissue biopsy specimen from screening will be used for a retrospective confirmation of EGFR mutation status by a central laboratory. The baseline biopsy as well as the optional tissue biopsy collected at progression will also be used to investigate mechanisms of response, primary resistance, and acquired resistance to rociletinib and MPDL3280A. Blood samples will be collected for pharmacogenomic and pharmacodynamics analyses. The pharmacogenomic blood sample will be collected predose on C1D1 for genomic deoxyribonucleic acid (DNA) purification. The DNA sample may be evaluated by next generation sequencing (NGS), and molecular alterations in germline and tumor DNA may be compared so that molecular alterations unique to the tumor that may modulate response or resistance to EGFR targeted therapy can be unambiguously identified. Pharmacodynamic blood samples will be collected and processed as described in Table 2 and Section 8.4.5.
Statistical Procedures	Statistical methods are described in Section 10.

THIS PAGE IS INTENTIONALLY LEFT BLANK

Table 1: Study CO-1686-032 Schedule of Assessments

				Trea	tment Period			
	Screening Period	Rociletinib 7-day Run- In- Period (Phase 1 only)	Cycle 1 combination therapy (21-day cycle) Cycle 2+ combination therapy (21-day cycle)			End of Treatment ^C	Follow Up	
Procedure ^A	Day -28 to Day 0	Day 1 ^B	Day 1 ^B	Day 4	Days 8 and 15 ±2 days	Day 1 ±3 days		
Informed consent	Х							
Documentation of EGFR mutational status ^D	Х							
Medical/oncology history ^E	Х							
Physical examination	Complete ^{F,G}	Limited ^H	Complete ^G	Limited ^H	Limited ^H	Limited ^H	Complete ^G	
ECOG performance status ^I	X ^F	Х	Х			Х	Х	
Vital signs ^J	\mathbf{X}^{F}	X	Х	Х	X	Х	Х	
Hematology (including reticulocytes) ^K	X ^F	Х	X		X	Х	X	
Coagulation tests ^L	\mathbf{X}^{F}							
Urinalysis ^M	Х							
Fasting_serum chemistry ^N	X ^F	Х	Х			Х	Х	
Fasting blood glucose ⁰				Х	X			
Serum pregnancy test ^P	Х						Х	
Hemoglobin A1c	Х					Odd cycles		
TSH, free T_3 and free T_4^Q	Х					Х	Х	

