3.4 Study Conduct and Duration of Patient Follow-Up

The study will comprise a Screening Period, and Treatment Period, and a Follow-up Period as outlined in Table 6. Please refer to Section 8 for additional details.

	Sign ICF						
COFFNINC DEDIOD	Screening Assessments						
SCREENING PERIOD	Up to 28 days before 1st dose of study drug (biops	sy within 60 days pi	rior)				
	Enrollment						
	Study assessments every 21 days. Additional ECG and glucose		Day 1				
TREATMENT PERIOD	monitoring during Cycle 1 (Day 4, Day 8, and Day 15). Tumor	Cycle 1	Day 4				
Oral rociletinib BID + IV	assessments every 2 cycles through Cycle 6 (end of Cycles 2, 4, and 6): every 3 cycles after Cycle 6 (end of Cycles 9, 12, etc.); and	Cycle I	Day 8				
MPDL3280A every 21days	at the EOT Visit. The frequency of tumor assessments may be		Day15				
	reduced after 2 years with approval of Medical Monitor.	Cycle 2 +	Day 1				
		Ļ					
	Disease Progression	Rociletinib and	/or MPDL3280A				
		treatment post-progression (Spons					
	(Optional post-progression tumor biopsy)	approval) with con	rotocol				
		↓ .					
	Treatment discontinuation						
END OF STUDY PERIOD	Follow-up Safety Assessment						
	28 days after last dose of study drug (rociletinib or MPDL3280A)						
	PK/ATA blood samples 120 days after last dose of MPDL3280A (see Table 2)						
	Follow-up for subsequent anticancer therap	vies and survival					
	Every 12 weeks						

Table 6:Study Schematic (CO-1686-032)

ATA, anti-therapeutic antibody; BID, twice-daily; ICF, informed consent form; IV, intravenous; PK, pharmacokinetics

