6.1.2 Management of Hyperglycemia

Rociletinib causes hyperglycemia in some people. Clinical experience with rociletinib suggests hyperglycemia generally occurs within the first 3 weeks of treatment, leading to the need for more intensive glucose monitoring during the first several weeks of the study in order to minimize the risk of symptomatic hyperglycemia. Because later onset of hyperglycemia is also possible with rociletinib treatment, regular monitoring of glucose and of symptoms of hyperglycemia will be required through the end of rociletinib treatment.

Fasting blood glucose (FBG) will be measured by local laboratories for the following visits: Screening/Baseline visit, Day 1 of the Run-in-Period (Phase 1 only), C1D1, C1D4, C1D8, C1D15, Day 1 of each cycle beginning with Cycle 2, and at the EOT Visit (Table 1). Investigators should use discretion on an individual-patient basis to determine the need for more frequent monitoring.

Diabetes and glucose intolerance are not contraindications to the use of rociletinib. Patients with pre-existing diabetes may require more frequent glucose monitoring and/or adjustments of diabetic medication. In addition to the scheduled local laboratory tests for FBG (see Table 1), patients with pre-existing diabetes should perform home monitoring at least once weekly (if not more frequently).

For patients who are not already monitoring their glucose levels, sites are strongly encouraged to implement *patient home monitoring of fasting urine glucose for Cycle 1 and Cycle 2*. If preferred, home monitoring of blood glucose is also acceptable. Patients should be educated to contact the site if they have any positive urine glucose test or a home blood glucose reading of > 160 mg/dL (> 8.9 mmol/L) and any time they experience symptoms that have correlated with rociletinib-induced hyperglycemia, including increases in nausea, vomiting, anorexia, diarrhea, and/or fatigue. Symptoms more commonly associated with diabetes, such as polydipsia, polyuria, and polyphagia, rarely occur with rociletinib-induced hyperglycemia. Upon reports of positive home tests and/or symptoms suggesting hyperglycemia, local laboratory FBG tests should be performed.

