6.2.5 Management of Endocrine Toxicity (Hypothyroidism)

Hypothyroidism has been associated with the administration of MPDL3280A.

Patients with unexplained symptoms such as fatigue, myalgias, impotence, mental status changes, or constipation should be investigated for the presence of thyroid, pituitary, or adrenal endocrinopathies, as well as for hyponatremia or hyperkalemia. An endocrinologist should be consulted if an endocrinopathy is suspected. Thyroid-stimulating hormone (TSH) and free T4 levels should be obtained to determine whether thyroid abnormalities are present. TSH, prolactin, and a morning cortisol level will help to differentiate primary adrenal insufficiency from primary pituitary insufficiency.

Hypothyroidism should be managed according to Table 15.

 Table 15:
 Management Guidelines for Hypothyroidism

Description	Management
TSH elevated, asymptomatic	Continue MPDL3280A;
	• Start thyroid replacement hormone (as per institutional guidelines);
	Monitor TSH weekly.
TSH elevated, symptomatic	Hold MPDL3280A;
	• Consider referral to an endocrinologist;
	• Start thyroid replacement hormone (as per institutional guidelines);
	• Monitor TSH weekly;
	• Restart MPDL3280A when symptoms are controlled by thyroid replacement and TSH levels are decreasing.

TSH, thyroid-stimulating hormone.

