8.4.2.2 Clinical Laboratory Investigations

Blood for safety evaluations will be analyzed by a local laboratory to inform patient treatment decisions, and results must be reviewed by the Investigator before administration of rociletinib and/or MPDL3280A. Additional tests may be performed at the Investigator's discretion. The panels of laboratory tests to be performed are shown below:

Hematology: Hematology assessments include hemoglobin, hematocrit, WBC and differential (with ANC), reticulocyte count, and platelet count. Hematology results must be reviewed by the Investigator before administration of rociletinib and/or MPDL3280A.

Patients known to require concomitant therapy with anticoagulants such as warfarin should also have INR monitored throughout the study.

Serum Chemistry: Serum chemistry assessments include total protein, albumin, creatinine, BUN or urea, total bilirubin, alkaline phosphatase, ALT, AST, total cholesterol, fasting glucose, sodium, potassium, magnesium, chloride, calcium, phosphorus and uric acid.

In addition separate assessments of fasting glucose; hemoglobin A1c; TSH and free T_3 and T_4 ; will be performed as described in Table 1.

Urinalysis: Urinalysis will be performed on freshly voided clean sample by dipstick for protein, glucose, blood, pH, and ketones per the schedule of evaluations. If dipstick findings are abnormal, then a microscopic evaluation will be performed to assess the abnormal findings. Urinalysis is scheduled at screening only.

Serum ß-hCG Pregnancy Test (Local Lab): Performed on females of childbearing potential \leq 7 days before first day of study treatment and at the EOT Visit. If the serum pregnancy test results are not available on first day of study treatment, a urine pregnancy test can be performed on first day of study treatment to confirm that the patient is not pregnant before dosing. A negative result must be confirmed by a physician before the first dose of either study drug can be administered. Both values should be entered in the eCRF.

Laboratory reports will be reviewed by the Investigator or delegated physician who will then comment on out-of-range parameters and assess clinical significance. Clinically significant abnormalities and associated panel results, as well as results of any additional tests performed as follow up to the abnormalities, will be documented on the eCRF as an AE.

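### Potassium and magnesium are to be kept in range on rociletinib, but without a run-in neither is scheduled on treatment until Cycle 2 Day 1 (day 22)

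*Combined protocol and SAP*

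**What the plan says.** Section 6.1.1 requires normal potassium and magnesium at enrollment and adds that "these electrolytes should be maintained within range during rociletinib treatment, using supplementation if necessary". It gives no testing frequency.

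Both analytes belong to the serum chemistry panel; Section 8.4.2.2 and Table 1 footnote N list "sodium, potassium, magnesium, chloride, calcium, phosphorus and uric acid". In Table 1 the row "Fasting_serum chemistry" is marked at screening, Run-in Day 1 (Phase 1 only), C1D1, Day 1 of Cycle 2 onward and End of Treatment. The C1D4 and C1D8/C1D15 cells are empty. Table 6 describes extra "monitoring during Cycle 1 (Day 4, Day 8, and Day 15"), and the extra items are ECG and glucose only.

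Three other routes to an electrolyte test exist:

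- **Triggered:** Table 9 says "Test serum potassium, calcium, phosphorus and magnesium", once QTcF is at least 501 msec on two or more ECGs.
- **Symptom-driven:** Section 6.2.5 asks for a work-up of unexplained symptoms for endocrine disease "as well as for hyponatremia or hyperkalemia". Magnesium is not named.
- **Discretionary:** Section 8.4.2.2 states "Additional tests may be performed at the Investigator's discretion".

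**The concern.** The protocol sets an on-treatment goal but, for patients without a run-in, schedules no measurement during the first three weeks that would show whether the goal is met. Those weeks matter: Section 1.3.1 says QT prolongation is absent on Day 1, builds up over several days, is typically visible by Day 15 and then holds steady. A day-22 value still falls in the period of risk, but after the effect has usually appeared.

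The sponsor already treats the two electrolytes as relevant and correctable. They are an entry criterion, a maintenance goal and a Table 9 action. Patients may take supplements to qualify, and no scheduled Cycle 1 test checks that those patients stay in range.

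Gastrointestinal loss and poor intake are plausible causes of a fall. In Table 4, at 500 mg BID HBr, treatment-related nausea occurred in 6 of 18 patients, diarrhea in 4, decreased appetite in 4 and vomiting in 3. Section 6.1.2 has patients call the site for such symptoms ("including increases in nausea, vomiting, anorexia, diarrhea, and/or fatigue"), but the test it names is glucose. Section 6.2.3 names liver function tests for unexplained nausea or vomiting.

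What is at stake is an undetected, correctable low potassium or magnesium while QTc is rising. The primary endpoint, sample size and futility rules are not affected.

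**Working it through.** The plan gives no figure to reproduce. The check reads the schedule and counts days.

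**1. Which visits carry what (Table 1)**

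| Visit | ECG | Hematology | Fasting glucose alone | Chemistry (K, Mg) |
|---|---|---|---|---|
| C1D1 | yes | yes | no (within chemistry) | yes |
| C1D4 | yes | no | yes | no |
| C1D8, C1D15 | yes | yes | yes | no |
| C2D1 | yes | yes | no (within chemistry) | yes |

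The reading does not rest on one table row. Chemistry already includes fasting glucose, so a separate glucose row for Days 4, 8 and 15 would be redundant if chemistry were drawn then. Table 13 (Section 6.2.3) describes standard liver monitoring as three-weekly and predose, and those tests are in the same panel. Table 6 agrees.

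**2. Day of the first scheduled on-rociletinib value**

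Inputs: 21-day cycles (Section 8.2); a ±3-day window from Cycle 2 (Section 8); assessments before dosing where applicable (Table 1 footnote A); no run-in in Phase 2 (Section 3.3); a 7-day run-in in Phase 1 (Section 3.2).

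- No run-in: C1D1 is rociletinib day 1, predose. C2D1 = 1 + 21 = day 22, range 19 to 25. The interval between the two samples is 21 days (18 to 24).
- Section 8.1 lets a Phase 2 site skip C1D1 chemistry if it was done up to 3 days earlier, so the interval can reach 24 + 3 = 27 days.
- With run-in: C1D1 = 1 + 7 = day 8, which is one on-treatment value. C2D1 = 8 + 21 = day 29, range 26 to 32.

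In both phases, 0 of the 3 later Cycle 1 ECG visits has a scheduled potassium or magnesium value.

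**3. Patients affected**

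- Phase 2: 75/93 = 80.6%.
- Section 3.2.3 allows a safety cohort of up to 6, possibly without a run-in. If all 6 are treated that way: 81/93 = 87.1% if they are among the 18 Phase 1 patients, or 81/99 = 81.8% if they are additional.

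**4. What the safety data show (Tables 3 and 4, Study CO-1686-008)**

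- Treatment-related QT prolongation at 500 mg BID HBr: 0/18. Exact 95% upper limit = 1 − 0.025^(1/18) = 18.5%.
- At 625 mg BID HBr: 2/17 = 11.8%.
- All doses and formulations: 12/148, of which 5 + 3 = 8 were at 750 or 1000 mg BID HBr. The pooled figure therefore says little about 500 mg BID.
- Treatment-related hypokalemia SAE: 1/148, at 625 mg BID; 0/18 at 500 mg BID.

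**The case against.** The strongest reply is that the schedule looks deliberate. To a three-weekly base the sponsor added early visits for the two toxicities it singled out, with triplicate ECGs for QT and fasting glucose for hyperglycemia. QTc, the outcome of concern, is measured directly on Days 1, 4, 8 and 15. Section 6.1.1 says should, names no frequency, and so is not breached by Table 1.

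The safeguards are also real. Both electrolytes must be normal at entry. QTcF above 450 ms, resting heart rate below 55 and a long-QT history are excluded. QT-prolonging drugs are to be avoided, and exceptions need an agreed ECG plan. ECGs are read locally for patient management. An investigator who sees QTc rising below 501 msec is free to test.

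Nor is there a signal. Neither hypokalemia nor hypomagnesemia appears in Table 4, which lists treatment-related events in at least 5% of patients, and Table 3 has no hypomagnesemia SAE. The yield of the added tests is unknown.

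Most of this stands. It rules out calling the schedule a contradiction or a demonstrated hazard, and the patient counts describe who follows the schedule, not who has been shown to be at added risk. It does not close the gap. ECGs show that QTc has moved, not whether a low electrolyte is contributing. Entry values do not speak for weeks 1 to 3. Discretion is not a schedule. And 18 monotherapy patients leave an upper limit of 18.5% and do not address the combination.

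**Conclusion.** The concern holds as a gap in safety monitoring. Without a run-in, no potassium or magnesium value on rociletinib is scheduled before day 22 (19 to 25), for up to 75 Phase 2 patients and possibly 6 more. A patient treated exactly as written could carry a correctable low value through the period when QT prolongation usually appears. Phase 1 patients with a run-in have one earlier value, on day 8.

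The conclusion assumes that C1D1 chemistry is drawn before dosing and counts scheduled tests only; discretionary, symptom-driven and triggered tests may come sooner. No size of harm can be given, because the documents report no Cycle 1 electrolyte course. The change is worth making because it is cheap and protects patients.

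**What to change.** In Table 1, add potassium and magnesium to the local-laboratory bloods at C1D8 and C1D15, in both phases. State in Section 6.1.1 that the results are reviewed with that visit's ECG and corrected if out of range. Amend Table 6 and Section 8.4.2.2 to match. Testing at C1D4 is optional.

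The cost is two analytes at two existing visits. Hematology and fasting glucose are already drawn on both days, so no new visit or venipuncture is needed. Endpoints, sample size, futility rules and the planned laboratory summaries (Section 10.2.5.3) stay as they are.

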3.2.2 Assignment of Dosing Cohorts

Specific doses of rociletinib will be administered in combination with a fixed dose of MPDL3280A. Combination doses of rociletinib with MPDL3280A will be defined for each Dosing Cohort enrolled during the Dose Finding Phase, and currently two potential Dosing Cohorts are planned (see Table 5). The first Dosing Cohort will be 500 mg BID rociletinib and 1200 mg MPDL3280A on Day 1 of each 21-day cycle. At minimum, 3 patients will be enrolled into this cohort. If this combination dose is determined to be safe and tolerable, no further dose modifications for either drug will be made. Based on emerging safety and evaluable PK and/or pharmacodynamics data, the CSC may evaluate additional doses or schedules of rociletinib.

Cohort	Rociletinib Dose	MPDL3280A Dose
1	500 mg PO BID	1200 mg IV every 3 weeks
-1	375 mg PO BID	Day 1 of each 21-day cycle

Table 5:Phase 1 Dosing Cohorts

BID, twice daily; IV, intravenous; PO, oral.

A modified toxicity probability interval (mTPI) method (Appendix H) will be used to guide decisions on assignment of patients to different Dosing Cohorts. Compared with the 3+3 design, the mTPI method reduces the risk of exposing patients to doses above the MTD, which is defined as the acceptable daily oral dose with estimated probability of toxicity closest to 33%. The mTPI design is a model-based approach that has a pre-specified decision matrix that recommends escalating, reducing or maintaining the same dose or stopping dose escalation, based on the number of DLTs observed in the dose level under evaluation. Consequently, patients enrolled into the trial can be allocated to appropriate doses without conducting additional computations.

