3.3 Dose Expansion Phase (Phase 2)

The Dose Expansion Phase will be conducted in two patient cohorts (see also Figure 1):

Group A: EGFR TKI treatment-naïve and chemotherapy-naïve patients.

Group B: Patients who have progressed after at least 12 weeks of treatment with a prior firstor second-generation EGFR TKI (ie, erlotinib, gefitinib, afatanib), regardless of T790M mutation status.

The Dose Expansion Phase will be used to assess the RP2D of the combination of rociletinib and MPDL3280A for preliminary efficacy and pharmacodynamics effects, in addition to safety and tolerability, in these patient populations. For the Dose Expansion Phase, there will not be a Run-in-Period; rather, treatment will begin with both rociletinib and MPDL3280A on Cycle 1 Day 1 (C1D1). Patients will receive daily oral BID doses of rociletinib (RP2D) and IV doses of MPDL3280A on Day 1 of each cycle, in consecutive 21-day cycles. Patients will be evaluated regularly for safety and efficacy according to the Schedule of Assessments (see Table 1). For further details on the planned assessments and analyses of safety, PK, efficacy and pharmacodynamics, please refer to Sections 8.4.2-8.4.5.

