5.7 Dose Modification Guidelines

5.7.1 Study Treatment Dose Reductions

5.7.1.1 Rociletinib Dose Reductions

From a starting dose of 500 mg BID rociletinib, up to two dose reductions are available (Table 7). No dose reduction below 250 mg is permitted. All dose reductions are permanent.

Current Dosage	Dose Reduction
500 mg PO BID	375 mg PO BID
375 mg PO BID	250 mg PO BID
250 mg PO BID	No further dose reduction allowed

Table 7:Dose Reductions for Rociletinib

BID, twice daily; PO, oral.

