	 Begin/continue maximum supportive care and adequate combination anti-emetic treatments (see Section 7.6.1 for guidance on avoiding QT-prolonging concomitant medication). Consider gastroenterology consult;
	 Hold both rociletinib and MPDL3280A until < Grade 1. Restart rociletinib at next lower dose. If no recurrent symptoms, restart MPDL3280A;
	• If Grade \geq 3 nausea/vomiting recurs, MPDL3280A should be discontinued.

Toxicity	Attribution to both agents
Ocular Toxicity:	Grade ≥ 2:
	 Hold both study drugs until < Grade 1 (dose delays longer than 14 days require discussion with the Medical Monitor);
	 Obtain ophthalmology consult; uveitis or episcleritis may be treated with topical corticosteroid eye drops;
	 Reintroduce rociletinib at a reduced dose when symptoms resolved to Grade ≤ 1. If no recurrent symptoms, restart MPDL3280A; MPDL3280A should be permanently discontinued for immune-mediated ocular disease that is unresponsive to local immunosuppressive therapy.
Laboratory abnormalities	Grade \geq 3 Laboratory abnormalities related to study drug that are asymptomatic and deemed by the Investigator not to be clinically significant
	 After discussion between Investigator and Medical Monitor, rociletinib dosing may be delayed, and treatment subsequently resumed at the current dose level or at a reduced dose. If abnormality persists > 7 days, MPDL3280A dosing may also be held and subsequently resumed at the same dose level when toxicity resolves to baseline grade plus one.
Liver toxicities	Grade \geq 3 AST, ALT, or bilirubin abnormalities (or AST or ALT \geq 10 × ULN in patients with hepatic metastases) related to study drug that are asymptomatic and deemed by the Investigator not to be clinically significant
	• Hold both study drugs until recovery Grade ≤ 1 ;
	 Initiate systemic steroids IV for 48 hours followed by oral taper;
	 Monitor LFTs QOD until decreasing, then weekly;
	 If resolved to baseline grade plus one (eg, if baseline Grade 1, then Grade 2) resume MPDL3280A dosing;
	 If AE persists permanently discontinue MPDL3280A.
Other Grade ≥ 3 non-hematologic or Grade 4	 Hold rociletinib and MPDL3280A until recovery to Grade ≤ 1 and then restart rociletinib at a reduced dose and MPDL3280A at the same dose.
hematologic toxicity	 If the Grade 4 AE recurs (a second time), then MPDL3280A should be discontinued.
	 If the Grade 4 AE recurs (a third time), then rociletinib should be discontinued.

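### Table 9's QTc recurrence stop cannot be reached by a patient who starts rociletinib at 375 mg BID, and the restart it calls for at 250 mg is barred by Table 7

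*Combined protocol and SAP*

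**What the plan says.** Table 9 (Section 6.1.1) covers Grade 3 QTc prolongation, QTcF of 501 msec or more on at least two ECGs. The site interrupts study treatment until the interval returns to Grade 1 or baseline, then restarts one level down. The recurrence rule is: "If Grade 3 QTc prolongation recurs after 2 dose reductions, permanently discontinue study treatment". It carries no condition on starting dose. Footnote b, attached to the restart line and to both discontinuation lines, lets the patient resume after resolution if the Investigator and Medical Monitor agree that further treatment would help.

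Section 5.7.1.1 sets the available steps: "From a starting dose of 500 mg BID rociletinib, up to two dose reductions are available". It adds "No dose reduction below 250 mg is permitted" and "All dose reductions are permanent". Table 7 is keyed to current dose: 500 to 375, 375 to 250, and at 250 mg BID "No further dose reduction allowed".

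Section 3.2.2 says that "currently two potential Dosing Cohorts are planned". Table 5 lists them as 500 mg BID (Cohort 1) and 375 mg BID (Cohort -1). Under Section 3.3, Phase 2 patients start at the RP2D, whichever dose that turns out to be.

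**The concern.** The count of two reductions in Table 9 matches the ladder below 500 mg exactly, so it appears to have been written for that start alone. The protocol plans a second starting dose with a shorter ladder and applies the same count to it. For those patients the explicit recurrence stop has a precondition that can never be true, while the restart instruction points to a dose that does not exist.

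Section 1.3.1 states that rociletinib exposure is associated with QT prolongation, so this is an anticipated toxicity with its own stopping table. At stake is whether a site facing a recurrence at the lowest dose finds a defined instruction there or has to choose between two tables that disagree.

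**Working it through.** No sample-size arithmetic applies. The check counts steps in Table 7 and then walks the Table 9 rule event by event: if two reductions have been made and the event recurs, stop; otherwise restart one level lower.

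**Steps available (Table 7)**

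- 500 mg BID start: 500 → 375 → 250, so 2 reductions. This reproduces the figure in Section 5.7.1.1.
- 375 mg BID start: 375 → 250, so 1 reduction.

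**Walking Table 9 through successive Grade 3 QTc events**

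| Start | Event | Dose at event | Reductions so far | Result |
|---|---|---|---|---|
| 500 | 1 | 500 | 0 | restart at 375 |
| 500 | 2 | 375 | 1 | restart at 250 |
| 500 | 3 | 250 | 2 | Table 9 stop applies |
| 375 | 1 | 375 | 0 | restart at 250 |
| 375 | 2 | 250 | 1 | Table 9 calls for a lower dose; Table 7 has none; the stop needs 2 and only 1 was possible |

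The rule is coherent for QTc-driven reductions from 500 mg and breaks at the second event from 375 mg.

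**Patients already reduced for another toxicity.** Table 10 lets the Investigator consider a lower dose for glucose that is hard to control, and Table 18 calls for one in persistent Grade 2 diarrhea. Two cases follow for a 500 mg starter.

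- At 250 mg after two reductions for other reasons, with a first Grade 3 QTc event: no lower level exists, and nothing has recurred, so the recurrence stop is not met on its wording.
- One reduction for diarrhea (to 375), one for QTc (to 250), then a second QTc event: the total is 2, but only 1 was for QTc. Table 9 does not say which count applies. On the first reading the stop applies; on the second the patient is in the same position as the 375 mg starter.

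**Does another section settle it?** Section 5.7.4 sends the dose to the next level in Table 7 unless Sections 6.1 or 6.3 require discontinuation. For QTc, Section 6.1 is Table 9, so the reference is circular.

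**How likely is a 375 mg start?** Appendix H de-escalates after 2 or 3 DLTs in the first 3 patients. With true DLT rate p (assumed), the first-look probability is 3p²(1 − p) + p³:

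- p = 0.20: 3 × 0.04 × 0.80 + 0.008 = 0.104
- p = 0.33: 3 × 0.1089 × 0.67 + 0.0359 = 0.255
- p = 0.50: 3 × 0.25 × 0.50 + 0.125 = 0.500

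These cover the first look only. They show that Cohort -1 is a realistic branch, not a remote one.

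**The case against.** The best case against the point is that the patient is not left unprotected. Interruption at QTcF of 501 msec or more always applies. Footnote b makes resumption permissive, with Investigator and Medical Monitor both agreeing. Grade 4 QTc prolongation has its own line. A rociletinib hold beyond 14 days ends all study treatment unless the Medical Monitor allows longer (Sections 5.7.4 and 11.1). Section 11.1 also requires discontinuation for any event that the Investigator considers an unacceptable safety risk. All of this stands, so a reader who inferred that such a patient has no stop at all would be going beyond the text. What these provisions do not do is replace the recurrence stop: footnote b supplies no dose below 250 mg, a QTc that resolves within 14 days never reaches the hold limit, the Grade 4 line concerns a different event, and the Section 11.1 criterion is a judgement. Since the Medical Monitor must agree to each restart, divergence between sites is also not established.

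It is also fair that the main case is conditional. If 500 mg proves safe and tolerable, Section 3.2.2 plans no further change, and Cohort -1 may never open. In Phase 1, a 375 mg starter escalated to 500 mg under Section 5.7.4 would regain two steps; that needs approval and is not allowed in Phase 2.

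Two wider readings are tempting and not supported. The first is that the catch-all row of Table 18 has the same fault. It does not: "If the Grade 4 AE recurs (a third time), then rociletinib should be discontinued" counts occurrences of a Grade 4 event, not reductions, and can be reached from any starting dose. The second is that Section 5.7.4 overlooks 250 mg. It cites Table 7 and so carries the floor with it.

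**Conclusion.** The contradiction between Tables 9 and 7 is real for any patient who starts at 375 mg BID. A secondary gap exists for any patient who is already at 250 mg because of another toxicity.

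The size is limited and partly unknown. If 375 mg BID becomes the RP2D, all Phase 2 patients (up to 25 + 50 = 75) would be treated under the inconsistent wording. That is the number governed by the text, not the number who would meet the conflict. A reader might take the 7.6% with QTcF above 500 msec in Section 1.3.1, multiply by 75 and arrive at about 6 (0.076 × 75 = 5.7). The documents do not support that as an estimate of affected patients. The rate is pooled over formulations and doses up to 1000 mg BID, while Table 4 shows treatment-related QT prolongation in 0 of 18 patients at 500 mg BID HBr and 3 of 6 at 1000 mg. It also counts first events, which the tables handle consistently at 375 mg. No recurrence rate at 250 mg is given.

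The conclusion rests on reading both tables as written and on Cohort -1 being a genuine planned start, as Table 5 says. It is an internal inconsistency in a safety stopping criterion and should be corrected.

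**What to change.** Reconcile Table 9 with Tables 5 and 7, and with the sentence in Section 5.7.1.1 that describes reductions only from 500 mg, so that every planned starting dose, and every patient at 250 mg BID, reaches one consistent instruction after Grade 3 QTc prolongation. State in Table 9 whether reductions made for other toxicities count. Which clinical rule applies is for the sponsor to decide; this review does not propose one.

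The cost is amendment wording in Section 6.1.1 and Section 5.7.1.1, with the usual approvals. No visit, procedure or analysis changes. It is best done before any patient starts at 375 mg BID.
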